Appendix B: Forms

## Appendix C: Protocols for Substudy Procedures

Appendix D: Stratification for Substudy Participants

### I. INTRODUCTION

The patients entering the SOLVD trials are likely to represent an uncertain subset of the total population of patients with heart failure or left ventricular dysfunction at the participating clinical centers. The trial population is expected to be truncated with patients having the worst and best ventricular function excluded from the trials. Patients whose ventricular dysfunction or heart failure is related primarily to diastolic abnormalities without systolic dysfunction are excluded from the SOLVD trials, since marked systolic dysfunction is the key entry criterion. Other interesting and important subsets of patients, such as those with pulmonary edema at entry, are likely to be underrepresented in the SOLVD trials. In order to study the clinical course of a broader and more representative group of consecutively collected patients with heart failure at participating institutions and the relationship(s) of the SOLVD trial participants to this larger and less selected sample, a Registry of patients with left ventricular dysfunction will be developed. Vital status and clinical events will be determined at one year by a written questionnaire or telephone follow-up; longer term vital status will then be determined by periodic search of national death registries.

### II. AIMS OF THE REGISTRY

### A. Primary Objective:

The primary objective of the Registry is to study all-cause mortality at one, three and five years in a large (approximately 6,000) consecutive and relatively unselected cohort of patients with heart failure and/or with left ventricular dysfunction. The patients will be stratified according to symptoms, etiology of disease, ejection fraction and chest X-ray findings at entry into the Registry.

### B. Subsidiary Objectives:

The subsidiary objectives of the Registry are:

1. To study cardiovascular mortality at one, three and five years globally and after stratification according to symptoms, etiology of disease, ejection fraction and chest X-ray findings in the above populations.

2. To study morbid events at one year in the above population.

3. To relate other baseline covariates of prognostic importance to subsequent mortality and morbidity in the above population.

4. To characterize in greater detail clinical characteristics, echocardiographic abnormalities, arrhythmia status, functional capacity and neurohumoral levels and to correlate these detailed findings with subsequent mortality and morbidity in a stratified randomly selected sample of 1000 patients from among the patients entering the Registry.

5. To compare baseline characteristics and follow-up events of this relatively unselected population with those of the SOLVD Trials.

# III. PARTICIPATING CENTERS AND CAPABILITIES

All clinical centers collaborating in the SOLVD randomized trials will be invited to participate in the Registry. However, participation is not compulsory and individual centers may be free to decline. For example, if twenty centers are participating, each center will be required to enter and follow a minimum of 300 patients in the Registry. It is anticipated that at least 20% of the Registry patients at each center will also be in the SOLVD trials. Therefore, every participating center should be on target for recruitment for the SOLVD trials as a condition for participating in the Registry. In addition, each center must be willing to do high quality M-mode and 2-D echocardiograms, perform ambulatory monitoring and obtain a blood sample for renin and catecholamines in 50 patients randomly selected from their patients. Ability to do good quality echos is a condition for participation. The centers must be committed to following their patients in the Registry during the entire period of the study.

It is desirable to obtain Registry patients from one hospital site at each clinial center. Once a hospital is chosen to participate, all consecutive patients eligible for the Registry during the recruitment period of nine months must be enrolled. It is expected that around 6000 patients will be enrolled.

#### SOURCES OF PATIENTS IV.

Patients will enter the Registry as a result of: (1) screening consecutive exams in the laboratories of participating institutions (i.e., echocardiographic, radionuclide, and cardiac catheterization laboratories) to identify patients with an ejection fraction of 45% or less; or (2) by a survey of the consecutive hospital discharge records to identify patients with a diagnosis of congestive heart failure (CHF). In order to qualify for the Registry, patients identified from source (2) should have radiological evidence of CHF (or signs of pulmonary venus congestion) or an ejection fraction of 45% or less.

# V. ENTRY AND EXCLUSION CRITERIA

## Entry Criteria

Patients are eligible for the Registry if they either have an ejection fraction less than or equal to 45% or a diagnosis of congestive heart failure. The date of their logbook record or hospital admission must fall within the specified nine-month timeframe (for example, from January 1, 1988 to September 30, 1988). A diagnosis of congestive heart failure will be confirmed if the patient has radiologic evidence of CHF.

Descriptive statements consistent with heart failure which may appear in the report include:

- a) Statements related to pulmonary blood flow redistribution to upper lobes.
- b) Signs of pulmonary venous congestion
  - Basal or perihilar vascular blurring
    - Alveolar or pulmonary edema
    - Kerley B lines
    - Pleural effusion judged secondary to congestive heart
    - failure (to make this judgment may require correlation with clinical data).
- c) Cardio-thoracic ratio will be included whenever possible.

SOLVD Registry Protocol November 1987

In validating these heart failure criteria as positive, the interpretation on the chest X-ray report should be accepted if it is definite. Follow-up reports indicating clearing of congestive heart failure are helpful. Films should be reviewed by a physicianinvestigator whenever uncertainty exists.

Particular attention will be given to the subset of patients entering with the syndrome of pulmonary edema unrelated to acute myocardial infarction. Diagnosis should be (relatively) easily confirmed in this subset and the clinical history data on a large volume of patients with pulmonary edema could be a valuable contribution by this registry.

## Exclusion Criteria for SOLVD Registry

1) Non-valvular congenital heart disease.

2) Any noncardiac life-threatening disease likely to significantly shorten the patient's survival, including criteria 11 (cor pulmonale), 12 (advanced pulmonary disease), 13 (major neurologic diseases), 17 (renal failure), 18 (malignancies), 21 (significant primary liver disease), and 23 (other life-threatening disease) in the SOLVD trials protocol.

3) Failure to consent to the Registry.

Lack of a telephone or reliable means of contact/follow-up.

5) Myocardial infarction within 7 days. This patient can be included after 6 days have passed, if there is a qualifying chest X-ray or ejection fraction measurement made 7 or more days after the MI.

6) Cardiac surgery, PTCA, or ballon valvuloplasty within 7 days. This patient can be included after 6 days have passed, if there is a qualifying chest X-ray or ejection fraction measurement made 7 or more days after the cardiac surgery or PTCA.

Thus, the following exclusion criteria from the SOLVD trials protocol are not exclusion criteria for the Registry:

- History of intolerance to enalapril 1
- Currently taking ACE inhibitor and unwilling to discontinue 2
- Hemodynamically significant valvular or outflow tract 4 obstruction
- Constrictive pericarditis 5
- Syncopal episodes presumed to be due to life-threatening 7 arrhythmias
- Any major cardiac surgery likely 8
- Unstable angina pectoris 9
- 10 Uncontrolled hypertension
- Cerebrovascular disease 14
- Collagen vascular disease other than rheumatoid arthritis 15
- Suspected significant renal artery stenosis 16
- Immunosuppressive therapy 19
- 20 Active myocarditis
- Likely to be nonadherent (alcoholism, drug addiction, lack of 22 of a fixed address, etc.)
- Woman likely to bear children 24
- Other investigational drug protocols (except compassionate use) 25
- Failure to give consent for the SOLVD trials 26
- Lack of adherence or tolerance to medication 27
- Lack of adherence to placebo run-in 28

Note also that patients scheduled for cardiac transplantation are eligible for the ' Registry. Given all these differences, the patient population of the Registry will thus be broader and less restrictive than those eligible for the Trials.

- - - -

# Additional Exclusion Criteria for SOLVD Registry Substudy

- 1) Inability to attend clinic for a visit (e.g., geographical difficulties)
- 2) Failure to consent to the Registry substudy

All patients seen at the echocardiographic, radionuclide, and cardiac catheterization laboratories or admitted with a diagnosis of congestive heart failure are to be listed in consecutive chronological order in the SOLVD Registry Log. This log will contain the following information for each patient:

> Date Patient name (or internal hospital identification number) Source of recruitment Suitable for Registry: Yes or No If not suitable, why not

All patients entered in the log and considered suitable for the Registry must be contacted to obtain consent and have a Registry Baseline Form completed based on their medical records information. Those patients that refuse consent will only have the form completed through Question 5.5.

## VI. STUDY SIZE

It is expected that over 6,000 patients will be recruited into the Registry during the specified nine-month time period. In order to avoid a predominance of ischemic heart disease, special attempts to include patients with other etiologies may be required. These categories include the following:

- 1) Valvular heart disease with EF  $\leq$  45%
- 2) Primary diagnoses of idiopathic cardiomyopathy and active myocarditis.

3) Unusual and specific causes, such as amyloidosis, hemochromatosis, hypertrophic hyperdynamic cardiomyopathy (so-called IHSS), diabetic cardiomyopathy, alcoholic cardiomyopathy, etc.

The period for collecting such unusual cases may be extended beyond the first nine months Registry collection and as long as 1991. A decision regarding that will be made after the first nine months of recruitment.

The calculations in Table 1 examine the statistical power attained for comparing the mortality rates between two subgroups from the 6000 SOLVD Registry patients, under various assumptions. Comparisons of mortality rates can be done asymptotically with the test of difference of two binomial proportions (Rosner, p. 325). A two-sided test with a 0.05 level of significance is thus considered.

The following examples aid in the interpretation of the calculations in Table 1.

Case 1 would be for testing the difference in mortality between, for example, those with EF ≤ .40 (75% of Registry) vs. those with EF > .40 (25% of Registry). Power for this case is virtually unity.

Cases 2-3 and 4-6 look at testing the different mortality rates in a very rare subgroup vs. the entire rest of the Registry, under different relative risk situations. The rarer the etiology, the higher the relative risk needs to be, but a RR of 2 or greater has sufficient power to be detected, even after only one year. The power is greatly improved after three years.

Cases 7-9 look at testing the different mortality rates between two very rare subgroups, one that is seen in 2% of the patients vs. one that is seen in 1% of the patients. Informal estimates of prevalence of different etiologies suggest that amyloidosis would be seen in 20 per 1000 patients (2%), hemochromatosis would be seen in 10 patients per 1000 (1%), diabetic cardiomyopathy in 6-8%, alcoholic cardiomyopathy in 7-10%, post-partum in 2%. These cases need three years' worth of data to be tested with reasonable power, even with a relative risk of 2.

Cases 10-11: With 6000 persons in the Registry, it is not unreasonable to expect roughly 1000 patients with idiopathic cardiomyopathies. If this group is divided by tertiles of EF into low, intermediate and high EF, one would like to compare the mortalities between the high EF group and the low EF group. Assuming a relative risk of 3 provides power close to 1, while with a relative risk of 2, the power is virtually one at the three-year comparison.

				One-ye	ear		Power
Case #	n	m	pl	p2	RR	@1-year	@3-year
1	4500	1500	.12	.05	1/2.4	1.00	1.00
2	5900	100	.12	.24	2.0	.90	1.00
3	5900	100	.12	.18	1.5	.45	.77
4	5950	50	.12	.24	2.0	.69	.94
5	5950	50	.12	.30	2.5	.86	1.00
6	5950	50	.12	. 36	3.0	.99	1.00
7	120	60	.20	.30	1.5	.33	.58
8	120	60	.20	.40	2.0	.81	.97
9	120	60	.12	.24	2.0	.54	.87
10	333	333	.05	.15	3.0	.99	1.00
11	333	333	.06	.12	2.0	.77	.99

Table 1 One-year and three-year power for comparison of mortality rate between various Registry subgroups

Key: n = sample size in first subgroup m = sample size in second subgroup pl = 1-year mortality rate in first subgroup p2 = 1-year mortality rate in second subgroup RR = relative risk of second to first subgroup Thus, it is clear from the above examples that a sample size of 6000 patients in the Registry is quite adequate for comparison of mortality rates between various subgroups, especially after three years but in several cases even after one year.

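### Section VI says a relative risk of 2 has sufficient one-year power in a very rare subgroup, but Table 1 gives .69 for 50 patients; the claim holds at about 100

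*Protocol*

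**What the plan says.** Section VI sets out power for comparing mortality between two subgroups of the 6000 patients. The test is given: "Comparisons of mortality rates can be done asymptotically with the test of difference of two binomial proportions", and "A two-sided test with a 0.05 level of significance is thus considered".

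The text then explains the rows of Table 1 in groups. For the group at issue: "Cases 2-3 and 4-6 look at testing the different mortality rates in a very rare subgroup vs. the entire rest of the Registry". It remarks that rarer etiologies need a larger relative risk, but goes on to say that "a RR of 2 or greater has sufficient power to be detected, even after only one year", and adds that power is much better at three years.

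Table 1 is headed "One-year and three-year power for comparison of mortality rate between various Registry subgroups". Its columns are subgroup sizes n and m, one-year rates p1 and p2, relative risk, and one-year and three-year power. The two rows in this group with a relative risk of 2.0 are:

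- Case 2: "5900 100 .12 .24 2.0 .90 1.00"
- Case 4: "5950 50 .12 .24 2.0 .69 .94"

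Case 5 (n = 5950, m = 50, .12 against .30) is given one-year power .86.

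The next paragraph of Section VI says that Cases 7 to 9 need three years of data for reasonable power, even at a relative risk of 2. Case 8, at .81 after one year, is in that group.

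**The concern.** The sentence makes a relative risk of 2 a floor that is enough at one year for the very rare subgroups shown, with no lower limit on subgroup size. Case 4 is one of those subgroups, and its printed power is .69: a true doubling of one-year mortality would be missed about 3 times in 10.

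The wording also conflicts with the protocol's own usage. Case 8 at .81 is placed among the cases that must wait for three years, while Case 4 at .69 falls under a statement of sufficiency at one year.

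What is at stake is how one-year results in small etiologies are read. One-year mortality is part of the primary objective (Section II.A), and a relative risk of 2 called detectable at that point invites too much confidence in a null result from about 50 patients.

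**Working it through.** **Inputs.** All are from Section VI and Table 1: two-sided 5% test of two binomial proportions; total 6000; p1 = .12; p2 = .24 for a relative risk of 2. The protocol does not print its power formula. I used the standard one, with pooled variance under the null and unpooled variance under the alternative:

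power = Φ{ (|p1 − p2| − 1.96·√[p̄(1 − p̄)(1/n + 1/m)]) / √[p1(1 − p1)/n + p2(1 − p2)/m] }, with p̄ = (n·p1 + m·p2)/(n + m).

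**Reproducing the one-year column.**

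| Case | Stated | Computed |
|---|---|---|
| 1 | 1.00 | 1.000 |
| 2 | .90 | .901 |
| 3 | .45 | .454 |
| 4 | .69 | .685 |
| 5 | .86 | .915 |
| 6 | .99 | .986 |
| 7 | .33 | .327 |
| 8 | .81 | .806 |
| 9 | .54 | .541 |
| 10 | .99 | .991 |
| 11 | .77 | .773 |

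Ten of the 11 entries agree to rounding, so this is very likely the formula used, and .69 for Case 4 is not a misprint.

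**Case 4 in full.** p̄ = (5950 × .12 + 50 × .24)/6000 = .121. Null standard error = √[.121 × .879 × (1/5950 + 1/50)] = .0463, and 1.96 times this is .0908. Alternative standard error = √[.12 × .88/5950 + .24 × .76/50] = .0605. Power = Φ[(.12 − .0908)/.0605] = Φ(.48) = .685. The exact binomial power of the same test is .679.

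**How power depends on subgroup size** (one year, .12 against .24, total 6000):

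| Patients in rare subgroup | One-year power |
|---|---|
| 50 | .685 |
| 60 | .748 |
| 70 | .800 |
| 80 | .841 |
| 90 | .875 |
| 100 | .901 |

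Section VI puts hemochromatosis at 10 per 1000, which is 1% × 6000 = 60 patients, hence about .75.

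**Relative risk needed with 50 patients.** At p2 = .264 (relative risk .264/.12 = 2.2) power is .80. At p2 = .294 (relative risk 2.45) it is .90.

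**Three years.** The protocol does not print its three-year rates. Assuming a constant annual risk, 1 − (1 − p)³ gives .319 and .561 for Case 4, and power .945 against the stated .94. All three-year entries agree within 2 points on this assumption.

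**Case 5.** With p̄ = .1215, 1.96 times the null standard error is .0909 and the alternative standard error is .0649. Power = Φ[(.18 − .0909)/.0649] = Φ(1.37) = .915, against .86 stated; the exact power is .919. The value .86 would fit p2 = .28 (.861) or m = 40 (.860). Two other methods come near .86 for Case 5: unweighted averaging of the rates (.848) and Fisher's exact test (.866). They give .585 and .566 for Case 4, where the table has .69, so neither is the table's method.

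**The case against.** The strongest reply is that nothing is hidden. The same sentence opens by saying that rarer etiologies need a larger relative risk, the next one says that power improves greatly by three years, and .69 is printed in the table. The protocol sets no power target, so calling .69 insufficient applies an outside convention. Fifty patients is also fewer than any etiology with a stated prevalence would supply; the rarest, at 1%, gives 60, and Sections VI and VIII allow rare etiologies to be recruited into 1991. Finally, the main analysis is a proportional hazards model of time to death, and no enrolment figure or decision rule rests on Case 4.

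Much of this stands as a limit on importance. It does not remove the inconsistency. The opening clause is followed by a contrast that sets a relative risk of 2 as enough, without a size limit. The protocol's own handling of Case 8 at .81 supplies a standard that .69 does not meet. At 60 patients power is still only about .75.

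Two stronger readings are tempting, and the protocol does not support them. A reader might infer that the closing statement, that "a sample size of 6000 patients in the Registry is quite adequate for comparison of mortality rates between various subgroups", is also wrong, because Case 7 reaches only .58 at three years. But that sentence goes on to stress the three-year comparisons and confines its one-year claim to several cases, and it does not say that every row is well powered. Restricting it to relative risks of 2 or more would not help either: Cases 4, 9 and 11 all have a relative risk of 2, with one-year powers of .69, .54 and .77. A reader might also take Case 5 as a second overstatement. It goes the other way: the printed value is lower than the inputs imply, .86 and .915 lead to the same conclusion at a relative risk of 2.5, and a slip in typing or in reading the page cannot be excluded.

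**Conclusion.** The point holds as a misstated power property in one sentence. At one year a relative risk of 2 against a 12% rate has about 90% power with 100 patients in the rare subgroup, about 80% with 70, about 75% with 60 and 69% with 50. The general claim is therefore sound near 100 patients and overstated near 50. Three-year power at 50 patients is adequate (.94), so the sample size is not in question.

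Case 5 is a secondary query: about 5.5 points too low for its printed inputs, with no effect on any conclusion.

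The one-year figures rest on the protocol's own rates and test, and on a formula inferred from its match to ten of 11 rows. The three-year check also assumes a constant annual risk.

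**What to change.** Replace the general claim with one tied to subgroup size, for example: at one year, a relative risk of 2 has about 90% power with 100 patients in the rare subgroup, about 80% with 70 and 69% with 50; with 50 patients a relative risk of about 2.2 is needed for 80% power, and a relative risk of 2 needs the three-year data (power .94).

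Check Case 5 against the source calculation. If the printed inputs are right, correct the one-year power to .91–.92; if p2 or m is the misprint, correct that input.

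Leave the closing sentence of Section VI as it is.

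The cost is one sentence and one table cell. Enrolment, endpoints and analysis do not change; the stated one-year power for the smallest subgroups becomes less favourable.

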f) Chest X-ray and electrocardiogram. If not available from the preceding 90 days.

VIII. PERIOD OF PATIENT ACCESSION

The timetable for the SOLVD Registry is as follows:

	YEAR 1 December 1, 1987 - November 30, 1988
Dec. 1, 1987 - Dec. 31, 1987	Phase-in month. Major activities include training session for clinic personnel and quality control for substudy procedures.
Jan. 1, 1988 - Sept. 30, 1988	Nine-month recruitment period
Oct. 1, 1988 - Nov. 30, 1988	Two-month phase-down. Major activities include completing data col- lection of recruitment, evaluating continuation of recruitment of rare etiologies and planning for YEAR 2 follow-up activities.
	YEAR 2 December 1, 1988 - November 30, 1989
Mailing of que	estionnaire on vital statistics
	YEAR 3 December 1, 1989 - November 30, 1990
Vital status a	ascertained by the Coordinating Center with national death registries.
ч.	YEAR 5 December 1, 1991 - November 30, 1992
Vital status a	ascertained by the Coordinating Center with national death registries.
As shown in th	he timetable, patients with the more common etiologies will be enrolled

As shown in the timetable, patients with the more common ethologies will be enfolded during a 9-month period. Since only a few patients with the rarer ethologies (e.g., active myocarditis or specific cardiomyopathy) will be identified at each center per year, patients with these underlying diseases will be recruited until June 1991. A flow diagram for the SOLVD Registry is included in appendix A1.

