# Appendix D STRATIFICATION FOR SUBSTUDY PARTICIPANTS

It is expected that the vast majority of the participants eligible for the SOLVD Registry will have ischemic or hypertensive heart disease, and that about 5-10% would have cardiomyopathies or other "rare" etiologies. Thus, of the 6000 expected participants for the Registry, approximately 300-600 participants would be of the "rare" etiologies, and 5400-5700 would be of the more common etiologies.

The Registry has the potential to provide valuable clinical history information on the so-called "rare birds" of congestive heart failure. Given the interest in obtaining complete and detailed baseline information on these patients, the computer program for identifying those patients to be included in the Registry Substudy will essentially sample the Registry participants with two different sampling proportions: 100% of the rare etiologies would be included in the Substudy, and somewhere around 7-13% (approximately 400-700 participants) of the ischemic heart disease participants would be included in the Substudy, to roughly complete the 1000 patient desired.

Essentially, the Substudy subsample is a stratified random sample of the Registry sample, with two strata (ischemic heart disease, other) with different sampling proportions (.07-.13, 1.00, respectively).

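### Section VI expects about 1000 idiopathic cardiomyopathies among 6000 patients, but Appendix D expects 300-600 for all cardiomyopathies and rare etiologies together, so the power of Cases 10-11 and the 100% Substudy sampling rule rest on incompatible inputs

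*Protocol*

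**What the plan says.** Section VI (Study Size) bases Cases 10-11 of Table 1 on the statement that "it is not unreasonable to expect roughly 1000 patients with idiopathic cardiomyopathies" in a Registry of 6000. It continues: "If this group is divided by tertiles of EF into low, intermediate and high EF". The high and low thirds are compared at 333 patients each. Table 1 states these powers:

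- Case 10 (one-year mortality .05 against .15): .99 at one year, 1.00 at three years.
- Case 11 (.06 against .12): .77 at one year, .99 at three years.

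Appendix D describes the same 6000 expected participants and says that "about 5-10% would have cardiomyopathies or other 'rare' etiologies", which it converts to 300-600 patients. It then fixes the Substudy selection rule: "100% of the rare etiologies would be included in the Substudy", together with about 7-13% of the ischemic patients, to reach roughly 1000. It names two strata, ischemic heart disease and other, so idiopathic cardiomyopathy falls in the stratum sampled at 100%. Sections III and IX put the Substudy load at about 50 patients per center, and Section III uses twenty centers as its example.

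**The concern.** A single diagnosis in Section VI (1000 patients, 16.7% of 6000) is larger than the upper limit that Appendix D sets for the whole class containing it (600, or 10%). One part of the plan uses the larger figure to state power. The other uses the smaller figure to set a sampling rule.

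Whichever figure is right, something stated in the protocol fails. Either two rows of Table 1 promise more power than the cohort can give, or the selection program takes far more non-ischemic patients than the Substudy was sized for. The second failure matters because Section VII wants the Substudy to describe a relatively unselected population and to reveal biases in the chart data. That purpose needs a usable ischemic sample. The program assigns patients as they enter, so the fractions have to be right at the start.

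**Working it through.** **Inputs.** From Section VI: "test of difference of two binomial proportions", with "A two-sided test with a 0.05 level of significance is thus considered"; the rates and group sizes of Cases 10-11; about 1000 idiopathic patients. From Appendix D: 300-600 rare etiologies; sampling fractions of 1.00 and .07-.13. From Sections III, VII and IX: a Substudy of 1000, about 50 per center, and 20 centers as the example.

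**Formula.** With n per group, p̄ = (p1 + p2)/2 and d = |p2 − p1|:

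power = Φ{ [d − 1.96·√(2·p̄(1−p̄)/n)] / √([p1(1−p1) + p2(1−p2)]/n) }

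The protocol does not say how it obtained three-year rates. I assume 1 − (1−p)³, which turns .06 and .12 into .169 and .319, and .05 and .15 into .143 and .386.

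**Reproducing the plan at n = 333.**

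- Case 11: (.06 − 1.96 × .02218)/.02206 = .749, so power is .773 (stated .77). At three years it is .995 (stated .99).
- Case 10: (.10 − 1.96 × .02325)/.02292 = 2.374, so power is .991 (stated .99). At three years it is 1.000 (stated 1.00).

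The method therefore matches the plan for these two rows.

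**If Appendix D holds.** Even if every rare patient were idiopathic, there would be 300-600 of them, giving tertiles of 300/3 = 100 to 600/3 = 200. These are upper bounds on the group size.

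| | Stated (n = 333) | n = 200 | n = 100 |
|---|---|---|---|
| Case 10, 1 year | .99 | .918 | .656 |
| Case 10, 3 years | 1.00 | 1.000 | .978 |
| Case 11, 1 year | .77 | .555 | .316 |
| Case 11, 3 years | .99 | .938 | .692 |

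For example, Case 11 at n = 100 and one year: (.06 − 1.96 × .04047)/.04025 = −.480, and Φ(−.480) = .316.

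**If Section VI holds.** The 100% stratum contains at least 1000 patients, which is already the whole Substudy. Adding the other fraction:

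- lower end: 1000 + .07 × 5000 = 1350, or 1350/20 = 67.5 per center;
- upper end: 1000 + .13 × 5000 = 1650, or 1650/20 = 82.5 per center.

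**Appendix D against itself.** It is internally consistent: 300 + 12.3% of 5700 ≈ 1000, and 600 + 7.4% of 5400 ≈ 1000. The conflict is only with Section VI.

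**The case against.** The strongest reply is that these are loose planning figures in an observational registry. The primary objective is all-cause mortality in the whole cohort, Table 1 is offered as a set of examples, and nothing shows that 6000 was derived from Cases 10-11. Section VI's overall conclusion leans on three-year data, where Case 10 keeps power of .98 or more even at the smaller sizes. All of this stands and limits the weight of the point. It does not remove the contradiction: 1000 exceeds 600 by two thirds, both refer to the same 6000, and a fixed sampling fraction depends on which is true. The option to keep recruiting rare cases until 1991 does not reconcile figures that are both tied to that 6000.

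A reader might infer more than the documents support:

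- **That Cases 7-9 are also overstated.** Their groups of 120 and 60 total 180, which fits within 300-600. Appendix D gives no separate prevalence for those etiologies.
- **That 35-40% of the Registry is cardiomyopathy.** Adding Section VI's five listed prevalences (18-23%, or 1080-1380) to the 1000 gives 2080-2380. But Section VI calls these estimates informal and does not say that they exclude one another. The baseline form records concurrent etiologies as well as one primary etiology. No row of Table 1 uses the diabetic, alcoholic or post-partum figures. They would enlarge the excess if they do not overlap, but the point does not need them.
- **That Section VIII flatly contradicts Section VI.** It says that "only a few patients with the rarer ethologies (e.g., active myocarditis or specific cardiomyopathy) will be identified at each center per year". At 1-2%, a 300-patient center would see 3-6 cases of a given etiology, which is compatible. The tension comes mainly from the diabetic and alcoholic estimates.
- **That the Substudy would fall short or hold no ischemic patients.** Under Section VI's count, selection overshoots. Selected patients must also be able to attend, consent and have a good echocardiogram. No rates are given for these, so the number finally entering cannot be fixed.

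**Conclusion.** The point holds in a limited form and should be fixed. The expected etiology mix in Section VI cannot be reconciled with that in Appendix D.

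Under Appendix D, the loss is confined to Cases 10-11. It is largest for Case 11 (at most .32-.56 at one year and .69-.94 at three) and for Case 10 at one year (at most .66-.92). Under Section VI, the damage is to the Substudy's composition and to center workload: selection exceeds the target by 35-65% on idiopathic patients alone.

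The one-year powers rest only on the protocol's rates and test. The three-year powers also need the constant-annual-risk assumption, which returns the stated values to within .01 for these two cases. The per-center figures assume 20 centers. The documents do not show which prevalence is correct.

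**What to change.** Adopt one expected etiology distribution and use it in both Section VI and Appendix D. Then do one of the following.

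1. **If 5-10% is kept**, restate Cases 10-11 at the group sizes that it implies (no more than 100-200 per tertile), and amend the accompanying text on three-year power at a relative risk of 2. The sampling rule can stay.
2. **If about 1000 idiopathic cases is kept**, leave Cases 10-11 and lower the 100% fraction for the common cardiomyopathies. As an illustration with a non-ischemic stratum of 1000 and 7-13% of the other 5000, the fraction that returns a total of 1000 is (1000 − 650)/1000 = 35% to (1000 − 350)/1000 = 65%. Etiologies that really are rare could still be taken in full, with the fractions recalculated once their expected counts are stated.

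The cost is protocol wording, two recomputed table rows or one changed parameter in the selection program, and a less favourable result somewhere. Under the first option some stated powers fall. Under the second, detailed data are not obtained on every idiopathic case, which gives up part of Appendix D's aim.
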